Hypothesis 2 (H2): Relative to those treated at UC clinics, eligible 18-75 year-old prediabetes patients with uncontrolled CV risk factors at CDS clinics will have significantly more favorable trajectories in specific CV risk factors, including BP, lipids, smoking, HbA1c, and weight over a median 24-month follow up.

Hypothesis 3 (H3): Relative to those treated at UC clinics, eligible 18 to 75 year-old prediabetes patients at high CV risk treated at CDS clinics will have significantly more favorable patterns of metformin and statinuse over a median 24-month follow up.

Specific Aim 2. Assess the cost of the CDS intervention from the health system (payer) perspective through utilization analyses.

[figure not shown]
Hypothesis 4 (H4): After controlling for demographics and baseline clinical status, eligible patients with prediabetes treated in UC clinics versus CDS clinics will have significantly lower annual healthcare costs from the index date over a median follow up of 24 months.

Specific Aim 3: Describe critical facilitators and barriers for the prediabetes CDS implementation process, outcomes, and future dissemination using a mixed-methods approach.

Note that a previously included cost-effectiveness hypothesis (Hypothesis 5) was not tested due to lack of efficacy of the study intervention. Project results will provide a template for implementation of personalized CDS tools in rural and urban health settings, resulting in more efficient, effective rural healthcare that can be applied across many clinical domains, incorporates patient treatment preferences, and could substantially and sustainably improve the quality of CV care and clinical outcomes of millions of Americans with prediabetes in medically underserved areas.

Overview of Study Implementation Process and Design: The implementation process has four primary components (Figure 1): a) initial organizational engagement; b) adapting and piloting the Prediabetes CDS with Essentia primary care providers and patients; c) a group-randomized controlled study of the adapted CDSin 34 primary care clinics blocked on size and Essentia geographic service area; and d) evaluation of the implementation process and outcomes. It is critical to note that implementation is an iterative process, both in the adaptation

phase and during the randomized controlled trial of implementation and outcomes. Continuous feedback is provided to and

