Aim #2 – Health Care Costs (H4): Costs for this analysis include intervention costs and incrementalmedical care costs, defined from the health system perspective. Intervention costs include implementation and maintenance and training but exclude research and development costs. Standard accounting methods will be used to measure the cost of the CDS intervention. Medical care costs will include the cost of all prescribed medications and clinic services—including laboratory, lifestyle counseling, and physician services—incurred prior to and up to a 24-month post-index date period by participants in each study group, as indicated by Essentiabilling and clinical encounter data. Reliance on Essentia billing records for measuring medical care utilization may miss costs incurred in other health systems; however, this opportunity is expected to be equal across randomized study arms, and cross-system medical utilization at the clinic level is expected to be limited in this study population. For this reason, though, emergency visits and hospitalizations will be excluded from the analysis—and generally, these events are too infrequent in a sample of this size to accurately predict impact of the study intervention on hospital costs.

While market prices generally are a good estimate of the costs for medical services, the paid amount in this claims system is specific to Essentia at a particular time and may provide a biased view of costs between pre- and post-intervention periods. To address this, we will use Total Care Relative Resource ValuesTM (TCRRVs), which are a nationally standardized set of measures that have been endorsed by the National Quality Forum and are derived from Centers for Medicare and Medicaid Services (CMS) relative value units

(RVUs). TCRRVs extend CMS RVU measures to include utilization categories, such as laboratory services and medications, which do not have CMS RVU weights. Specifically, TCCRVs defined during the midpoint of patient accrual and follow-up (e.g., 2019) will be used to convert claims to represent U.S. dollars.

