Aim 2 Analytic Approach : Incremental medical costs will be estimated using standard health econometric methods. A generalized estimating equation (typically assuming a gammadistribution and log link function) will be used to estimate annualized costs by study arm while allowing clustering by clinicand controlling for demographics, time, and baseline clinical risk factors. The marginal effect of being assigned to an intervention clinic will provide an estimate of the incremental medical cost associated with the CDS intervention. The estimates assume that the CDS is implemented in a large health system with an EHR capable of exporting data to Web-based clinical algorithms. Aim 3 Analytic Approach: For measures not addressed in Specific Aim #1 and #2, measures of centrality will be computed for each of the RE-AIM measures. As an example, 24month CDS use rates will be determined to assess the completeness of implementation. Mixed models will assess changes in patient- and provider-reported outcomes using the Aim 1 analytic approach, with distributional and model modifications made as appropriate to each outcome. For patient and provider experience survey metrics we will describe the proportion of respondents indicating highest satisfaction for specific items at each time point and change over time for these items and for composite scales. Spearman correlations will be used to examine relationships between items, scales, and other study outcomes. Information first will be extracted and orchestrated into categories, themes, and patterns that emerge from and are grounded in data. Coding schemes will be developed and tested using the system recommended by Strauss and Corbin. Classification schemes and typologies will be used to identify and develop themes and concepts emerging from the data. Once coding has been completed and thematic and conceptualmaterial developed, we will also use descriptive data analysis to examine the importance and intensity of categories by their repetition within and across interviews, using counts and frequencies.

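### H4 counts cost from the index date, but the Aim 2 cost definition also takes in pre-index cost and the model reads H4 from the arm effect, so the outcome and its contrast need to be reconciled

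*Combined protocol and SAP*

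**What the plan says.** Three places bear on the H4 outcome.

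- **Specific Aim 2, Hypothesis 4.** Patients in usual care (UC) clinics, compared with those in CDS clinics, are expected to have "significantly lower annual healthcare costs from the index date over a median follow up of 24 months". The adjustment is given as "After controlling for demographics and baseline clinical status". Prior cost is not named.
- **Definition and Measurement of Variables, Aim #2 – Health Care Costs (H4).** Medical care costs are to include prescribed medications and clinic services "incurred prior to and up to a 24-month post-index date period by participants in each study group". The length of the earlier period is not stated. The next paragraph justifies standardised pricing on the ground that amounts paid "may provide a biased view of costs between pre- and post-intervention periods".
- **Aim 2 Analytic Approach.** A generalized estimating equation (GEE), typically gamma with a log link, models annualized cost by arm with clustering by clinic, "controlling for demographics, time, and baseline clinical risk factors". The estimand follows: "The marginal effect of being assigned to an intervention clinic will provide an estimate of the incremental medical cost associated with the CDS intervention". No arm-by-period term, baseline-cost covariate or restriction to post-index cost is named.

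The Aim 1 Analytic Approach, by contrast, names both a treatment-by-time interaction and the index value of the outcome as model terms.

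**The concern.** The hypothesis and the measurement section give different cost windows for the same test, and the model does not say which applies. The CDS cannot change cost incurred before a patient's index visit, and randomization makes the expected arm difference in that period zero. If pre-index cost sits in the outcome and H4 is read from the arm effect, the result averages a null period with the period of interest and is pulled toward no difference. A main effect for time does not prevent this. It absorbs the overall change between periods but still forces one arm effect on both.

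The direction matters. H4 predicts lower cost in UC, that is, higher cost under the CDS, so dilution makes a real cost increase easier to miss. The cost-effectiveness hypothesis was not tested, so H4 is the remaining economic hypothesis.

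**Working it through.** **No plan figure to reproduce.** The documents give no detectable cost difference, power or pre-index window for H4. The only power figures concern the H1 slope and do not bear on cost.

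**Inputs.** The post-index window is 24 months (Aim #2 measurement section). The pre-index window P is not stated, so a range is shown. A true post-index cost ratio of 1.10 is assumed for illustration. The expected pre-index arm difference is zero, by randomization.

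**Dilution if both periods are pooled under one arm effect.** With equal mean monthly cost before and after index:

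- share of the log ratio lost ≈ P/(P+24)
- pooled cost ratio = (P + 24 × 1.10)/(P + 24)

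| Assumed P (months) | Share lost | Pooled ratio when the true ratio is 1.10 |
|---|---|---|
| 3 | 3/27 = 11% | 29.4/27 = 1.089 |
| 6 | 6/30 = 20% | 32.4/30 = 1.080 |
| 12 | 12/36 = 33% | 38.4/36 = 1.067 |
| 24 | 24/48 = 50% | 50.4/48 = 1.050 |
| 36 | 36/60 = 60% | 62.4/60 = 1.040 |

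If each patient contributes one annualized pre-index record and one annualized post-index record with equal weight, the share lost is about 1/2 whatever P is.

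**Equal-cost assumption.** If total cost is pooled and monthly pre-index cost is c times the UC post-index cost, the share becomes Pc/(Pc+24). At P = 12 this is 9.6/33.6 = 29% for c = 0.8 and 14.4/38.4 = 38% for c = 1.2, against 33% for c = 1.

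**Check with the planned type of model.** A gamma, log-link GEE was simulated with 34 clinics of 194 patients (34 × 194 = 6,596, near the anticipated 6,600) and a true ratio of 1.10. There were 12 runs per scenario, so Monte Carlo noise is about 0.1. Share of the true log ratio recovered:

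| Annual records (pre + post) | Arm + period | Arm-by-period | Post-index only | Post-index, pre-index cost as covariate |
|---|---|---|---|---|
| 1 + 2 | 0.68 | 1.11 | 1.05 | 1.06 |
| 2 + 2 | 0.58 | 0.92 | 1.04 | 1.02 |
| 1 + 1 | 0.47 | 0.94 | 0.94 | 0.89 |

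The arm + period column agrees, within noise, with the expected 0.67, 0.50 and 0.50. The other three analyses show approximately no dilution.

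**Power, illustrative only.** None of these inputs is in the documents: 17 against 17 clinics of 194, annual patient CV 1.5, between-clinic SD 0.10 on the log scale, correlation 0.5 between a patient's years, and a two-sided 5% t-test on clinic mean log cost in place of the GEE. With Y years of cost, the clinic-mean variance is 0.01 + 2.25 × [1 + (Y − 1) × 0.5]/(Y × 194), and SE = √(2 × variance/17).

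- Post-index only (Y = 2): ln 1.10 = 0.0953, SE 0.0469, ratio 2.03, power about 0.50.
- P = 12 (Y = 3): ln 1.0667 = 0.0645, SE 0.0457, ratio 1.41, power about 0.28.
- P = 24 (Y = 4): ln 1.05 = 0.0488, SE 0.0450, ratio 1.08, power about 0.18.

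These show the direction and rough scale of the loss. They do not describe this trial's power.

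**The case against.** The strongest reply is that pooling was probably not intended. The hypothesis itself dates cost from index. The Aim #2 paragraph sits among the variable definitions and may only list which costs are captured, not how they enter the model. Its remark about comparing the two periods fits a baseline or a pre/post contrast better than one averaged outcome. A marginal effect can be derived from a model with an interaction, so the analytic paragraph does not exclude one. The covariate section defines time as years from index to later measurements, although it does so for the Aim 1 outcomes. The protocol also refers to an Appendix A on measuring the study variables, which is not in the text reviewed and might state the window.

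Much of this stands. A reader might infer that the plan does pool pre-index cost and will lose a third to a half of any cost difference. The documents do not support that. They do not clearly say that pre-index cost is pooled, and they give no window. The third-to-a-half range corresponds to an assumed 12 to 24 months, or to equally weighted pre and post records. Under a baseline or contrast reading the loss is zero.

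The reply does not remove the conflict. The measurement sentence is headed for H4 and says what the costs include. Neither the hypothesis nor the model names baseline cost as a covariate, and no interaction is named that would make the analysis a pre/post contrast. The benign readings are plausible, but they are not written down.

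**Conclusion.** The point holds as a conflict between stated rules with a conditional consequence. The hypothesis and the Aim #2 cost definition give different windows, and the analytic approach reads the incremental cost from arm assignment without resolving the difference.

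If the measurement and analysis sections are applied literally, the arm log cost ratio is diluted by about P/(P+24), assuming equal mean cost in both periods and no arm difference before index. That is 20% at an assumed 6 months, 33% at 12 and 50% at 24. If pre-index cost is only a baseline, or H4 is read from a pre/post contrast, there is no dilution. The power figures rest wholly on assumed inputs and carry no weight in this conclusion. The matter should be settled because it decides what H4 estimates and the repair is cheap.

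**What to change.** - **Aim #2 – Health Care Costs (H4).** Define the H4 outcome as cost from the index date to 24 months after it, and state that pre-index cost is not part of the outcome. State the length of the pre-index window and what it is for.
- **Aim 2 Analytic Approach.** Either model post-index cost only, with pre-index cost as a covariate if wanted, or, if both pre- and post-index records are kept, name the arm-by-period contrast as the H4 estimand in place of the arm main effect. Say what time means in this model.

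The cost is a few sentences in two sections. The data are already planned for collection, and either route is a standard form of the model already specified.

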Step F: Iterative Use of the Prediabetes CDS over a Series of Visits. A key design feature of this intervention is its repeated use at all office visits of eligible patients during the intervention period. The CDS is automatically activated at any visit during the study period for eligible patients and provides updated treatment priorities and recommendations at each visit. Pilot data indicate that eligible patients average 4-6 primary care visits during a 24 month period, assuring that nearly all intervention patients have at least 3 exposures to the CDS. The CDS can also be manually activated by the PCP. In our previous study, almost 70% of eligible PCPs maintained use of the CDS system. With strong support from Essentia leaders and PCP leaders, we expect similar use rates.

Prediabetes patients converting to diabetes will continue to receive appropriate CV risk reduction prioritization and evidence-based glucose and aspirin treatment recommendations, thus facilitating timely treatment transition for newly diagnosed diabetes and reducing the lag time often reported between conversion to diabetes and being clinically diagnosed and treated.

Implementation of the Prediabetes CDS Intervention: Key implementation stages include: organizational engagement; adapting, piloting, and refining the Prediabetes CDS; and implementing the Prediabetes CDS group-randomized study. Key informant interviews, focus groups, surveys, usability testing, EMR data, and continuous quantitative and qualitative feedback between researchers and stakeholders will be used to monitor the implementation process and outcomes.

Organizational Engagement: As part of the initial engagement process, Essentia leaders and PCP leaders have already provided letters of support for the prediabetes CDS. Further engagement with Essentia leadership, informatics personnel, and key providers will occur through in-person meetings, conference calls, informational meetings, and identification of critical personnel to participate in the development, adaptation, and piloting processes of this study.

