Aim #1- (a) Cardiovascular Risk Trajectories (H1): There is no validated CV risk engine developed with a prediabetes population. Therefore, we propose to use the ACC/AHA 10-year pooled CV risk engine to estimate annual rate of change in CV risk as our primary outcome. We will use the lipid equation for patients with lipid data available to calculate CV risk at the index and all post-index visits and, to minimize missing CV risk values, the BMI equation at the index and all post-index visits for the remaining patients. The BMI equation estimates higher CV risk relative to the lipid equation. Because the calculation method will be consistent across all visits within each patient this difference will not bias the estimated rate of change in CV risk. CV risk scores for each patient will be calculated at each primary care visit from the index through the entire follow-up period using available EHR data elements. As depicted in Figure 2 Step A, at each visit we will search for the most recent data elements, looking back over a period appropriate for each risk component (i.e., 12 months for BP values or medications, DM diagnosis, smoking, BMI; 48 months for lipids). H1 will be supported if the annual rate of change in CV risk scores from the index visit through the end of the follow-up period is lower (ie, less increase) among patients in the CDS relative to UC clinics; (b) Modifiable diabetes and CV risk factors (H2): Risk factors needed to calculate the CV risk scores (weight, systolic blood pressure, HDL-c, LDL-c, totalcholesterol, smoking), are extracted from EHR files as in Figure 2 Step A. H2 will be supported if annual rate of change in CV risk component trajectories are lower among patients in the CDS relative to UC clinics; (c) Metformin and statin use (H3): Data to assess drug treatment are from EHR files such as prescribed medications. The presence or absence of appropriate drug use will be assessed at each visit. H3 will be supported if appropriate drug use improves over the follow-up period among patients in the CDS clinics relative to UC patients.

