Measures of Covariates for Primary and Secondary Analyses: One predictor of CV risk, risk factor, and drug use outcomes is the binary indicator for study condition (CDS or UC). The second key predictor is time elapsed in years between the patient's index visit to each subsequent measurement. Several other measures merit consideration as dependent outcomes, moderators or mediators in primary analyses. These include (a) number of PCP patient encounters, (b) patient characteristics including demographics and pre-intervention clinical values and comorbidities (EHR ICD-10 diagnosis codes and problem lists), and (c) provider characteristics such as age, gender, type of provider, full-time or part-time work status,, specialty board certification status, and proportion of eligible study patients. Patient or provider characteristics may also be used to adjust for covariate imbalance introduced by clinic randomization.

Analysis Plan.

Aim 1 Analytic Approach. Aim 1 pertains to the effectiveness of the Prediabetes CDS intervention, predicting that it will improve the annual rate of change in CV risk (CVR) and individual risk factors relative to UC. Patients age 40-75 at index are included in the Aim 1 analyses because the CDS was programmed to deliver the intervention via treatment recommendations (Figure 2, Step B) to this age group. Rate of change outcomes (e.g., H1, H2) will be tested using random coefficients models in which all available index and post-index outcomes (H1 CV risk, H2 CV risk factors) will be predictedfrom fixed effects for clinic-randomized treatment group, years elapsed since index CVR, the treatment by years elapsed interaction and the index outcome value. Outcomes measured only once per person will follow the same approach, omitting predictors that incorporate years elapsed since index and where warranted including an offset for follow-up time.

Random clinic and patient intercepts will account for clustered observations as appropriate. The link function and error distribution for each model will be determined by the distribution of each outcome. The relationships between years elapsed and CV risk and risk factor outcomes are expected to be linear. The tenability of this assumption will be checked for each outcome and more complex relationships (e.g., non-linear, spline) modeled if warranted.

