The years elapsed parameter will estimate the annual rate of change in CV risk and risk factors among patients in UC clinics in the absence of intervention, while the treatment by years elapsed parameter estimates the difference in the annual rate of change among patients in the CDS relative to UC clinics. It is expected that CV risk will decrease, or increase at a slower rate, among patients in CDS relative to UC clinics. Similar patterns of improvement, or slower worsening, are expected for CV risk factors. Finally, the treatment group parameter is expected to estimate more appropriate pharmacologic use among patients in CDS compared to UC clinics.

2.2.6.1 H1 Sample size justification. We conducted a power analysis to estimate theminimum detectable slope of the treatment by time parameter (power=.80, α_2 =.05) given the anticipated sample size (15 CDS clinics, 7-11 providers per clinic * 25 patients per provider = 2625-4125 CDS patients, 3 CVR per patient).. The patient sample size was divided by the design effect, Neff = N / [1 + (n_{clus} – 1) ρ], to approximate the effective independent patient sample size (Neff) implied by clinic intraclass correlations (ICC) of ρ = .001-.02. The CVR sample sizes (Neff patient * 3 CVR/pt) were divided by the design effect implied by a patient ICC=0.80. The resulting effective CVR sample sizes were used to estimate the minimum detectable standardized linear regression coefficient (β_{CDS}) relative to β_{UC} =0. When ICC_{clin}=0.001, the minimum detectable β_{CDS} =0.044-0.055; when ICC_{clin}=0.005 β_{CDS} =0.061-0.070; and when ICC_{clin}=0.02 β_{CDS} =0.103-0.108.

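### The primary model uses the index value both as a year-0 outcome and as a covariate, so the model-based standard error of the slope difference can be modestly wrong in either direction

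*Combined protocol and SAP*

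**What the plan says.** All references are to the combined protocol and SAP.

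- **Outcomes and predictors** (Analysis Plan, Aim 1 Analytic Approach). Rate-of-change outcomes "will be tested using random coefficients models". The responses are stated as follows: "all available index and post-index outcomes (H1 CV risk, H2 CV risk factors) will be predictedfrom fixed effects for clinic-randomized treatment group". The remaining predictors are "years elapsed since index CVR, the treatment by years elapsed interaction and the index outcome value". No index-by-time term is listed.
- **Random effects** (same section). "Random clinic and patient intercepts will account for clustered observations as appropriate". No patient slope is named, and no robust variance is specified for Aim 1.
- **Test.** The text that follows takes the treatment-by-years coefficient as the difference in annual change between arms. That coefficient is the H1 test.
- **Measurement times** (Aim #1, Cardiovascular Risk Trajectories). "CV risk scores for each patient will be calculated at each primary care visit from the index through the entire follow-up period", and "at each visit we will search for the most recent data elements, looking back over a period appropriate for each risk component".
- **Visit rates.** Step F says that "eligible patients average 4-6 primary care visits during a 24 month period". Study Participants gives a median of 6 visits in 24 months and a follow-up of 26 to 38 months.
- **Planning values** (H1 Sample size justification). There are 3 scores per patient, and the score counts "were divided by the design effect implied by a patient ICC=0.80".

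**The concern.** The index score is a response in the year-0 row and also a predictor of itself in that row. In later rows it is an ordinary baseline covariate. The right coefficient differs between the two kinds of row, but the model allows only one. The compromise leaves almost no residual variance at index and much more afterwards.

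Random intercepts with a constant residual variance cannot represent that jump. A patient random slope can absorb part of it, but only by reading it as patients fanning out over time. In either case the reported standard error of the treatment-by-years term need not equal its true sampling error. The stakes are the type I error and power of H1. H2 uses the same model, and the Aim 3 and secondary analyses borrow the approach.

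**Working it through.** **1. The plan's own figures.** The minimum detectable slope is (1.96 + 0.84)/√n, with n = N/[1 + (N/15 − 1)ρ] × 3/(1 + 2 × 0.80). For N = 2625 and ρ = 0.001: 2625/1.174 × 3/2.6 = 2580, which gives 0.055 as stated. Over N = 2625-4125 the results are 0.046-0.055, 0.063-0.070 and 0.103-0.108 for ρ = 0.001, 0.005 and 0.02. The plan states 0.044-0.055, 0.061-0.070 and 0.103-0.108. The two small mismatches do not matter here, because this calculation includes neither the index covariate nor irregular timing.

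**2. Covariance left by dual use.** Take a standardised outcome, compound symmetry and r = 0.80. The right coefficient on the index value is 1 in the index row and 0.80 in later rows. With k scores the pooled value is g = [1 + (k − 1)r]/k.

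| | formula | k = 3 | k = 6 |
|---|---|---|---|
| pooled coefficient | g | 0.867 | 0.833 |
| index residual variance | (1 − g)² | 0.018 | 0.028 |
| post-index residual variance | 1 − 2gr + g² | 0.364 | 0.361 |
| index-post covariance | (1 − g)(r − g) | −0.009 | −0.006 |
| post-post covariance | r − 2gr + g² | 0.164 | 0.161 |

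For k = 3: 1 − 2(0.867)(0.80) + 0.867² = 0.364.

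**3. Effect on the standard error.** The measure is the model-based SE divided by the patient-robust SE of treatment-by-years. Data: 12,000 simulated patients, no true effect, no clinic effect, random visit times over 26-38 months. Slope SD is in outcome SDs per year and is assumed.

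| scores | slope SD | intercepts only, as written | intercepts only, covariate dropped | random slopes, as written | random slopes, covariate dropped |
|---|---|---|---|---|---|
| 3 | 0 | 0.917 | 0.993 | 1.113 | 1.000 |
| 6 | 0 | 0.967 | 0.998 | 1.121 | 1.008 |
| 3 | 0.1 | 0.876 | 0.958 | 1.100 | 1.000 |
| 6 | 0.1 | 0.892 | 0.918 | 1.070 | 1.001 |

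When the true slope SD is 0, the random-slope model as written fits a spurious SD of 0.23 (3 scores) or 0.13 (6 scores).

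A direct check on 400 null data sets of 300 patients (irregular visits, slope SD 0) agrees. The ratios were 0.97 for the plan with intercepts, 1.11 for the plan with random slopes, and 1.00 for random slopes without the covariate.

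**4. At the plan's visit rates.** Four to 6 visits in 24 months is 2-3 a year. With assumed Poisson or gamma-Poisson counts and at least one later visit, the ratios as written are:
- Intercepts only, slope SD 0: 0.960-0.987.
- Random slopes (gamma-Poisson counts, at 2 and 3 visits a year): 1.079 and 1.074 at slope SD 0; 1.018 and 1.000 at SD 0.1.

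**5. Type I error** = 2[1 − Φ(1.96 × ratio)]. Ratios of 0.960 and 0.987 give 6.0% and 5.3%. A ratio of 0.915 (3 scores) gives 7.3%, and 1.079 gives 3.4%.

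**6. Power under random slopes** = Φ(2.80 × SE_dropped/SE_written − 1.96 × ratio), with the effect set so that the model without the covariate has 80%. At the plan's visit rates the results are 72.0% and 72.9% (SD 0), and 76.3% and 78.1% (SD 0.1). At 3 scores they are 69.3% and 70.5%.

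Not all of the loss is miscalibration. At ratio 1.079 with equal true SEs, power would be Φ(2.80 − 2.115) = 75.3%; the rest of the fall to 72.0% is a larger true SE. At ratio 1.000 the whole loss to 78.1% is a true SE about 2% larger.

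**7. Where the error vanishes.** If all patients share one fixed schedule of 3 or more scores and only intercepts are fitted, the slope is estimated within patients. The covariate is constant within a patient and drops out, so the ratio equals that of the model without it (about 1.00 when slopes do not vary).

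**The case against.** **The supported reading is the mild one.** Only intercepts are named, and at realistic visit counts that means 5.3-6.0% in place of 5%. This largely stands. But 3 scores per patient is the plan's own power assumption, and a random coefficients model ordinarily implies random slopes, so the text leaves both readings open.

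**Under random slopes the test is conservative, and the error shrinks as true slopes vary.** This stands. With 3 scores the ratio falls from about 1.13 at slope SD 0 to 1.08 at SD 0.2; with about 4 later visits it falls from 1.12 to 1.04.

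**Other errors can be larger.** This also stands. With intercepts only, about 4 later visits and slope SD 0.2, the ratio is 0.74 as written and still 0.77 without the covariate. Under an extreme assumption that the look-back carries whole residuals forward, intercepts-only ratios are 0.46-0.78 as written and 0.46-0.84 after dropping it. Clinic clustering, absent from the simulations, multiplies the SE by √1.174 = 1.08 to √6.48 = 2.55 under the plan's own design effect.

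**Stronger readings to resist.**
- A reader might infer that the slope difference is biased. In the simulations, with visit patterns alike in both arms, it stayed essentially unbiased, and the documents do not show that visit patterns differ by arm.
- A reader might infer that a conservative model explains why the intervention was not found effective, as the note on Hypothesis 5 reports. The documents give neither the fitted random effects nor the estimate, so they cannot support this.
- A reader might infer that the SE is wrong in every case. Steps 4 and 7 show cases where it is not.

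**Conclusion.** The specification error is in the text of the primary model, and its mechanism follows from the plan's ICC under compound symmetry. Its size is minor to moderate, and its direction depends on a choice that the plan leaves open.

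- **Intercepts only, no true slope variation:** SE about 1-4% too small at the plan's visit rates, and about 8-9% at 3 scores.
- **Patient random slopes:** SE about 0-8% too large at those visit rates. At 3 scores it is about 10-13% too large for slope SD 0-0.1, and about 8% for SD 0.2.

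These figures rest on the planning ICC of 0.80, assumed visit times, count spread and slope SD, and no clinic effect. They concern calibration and some efficiency, not bias.

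**What to change.** 1. Use the index value once. Keep index and post-index values as outcomes and drop the index covariate. This costs no precision: the robust slope SE as written was 1.006-1.044 times that with the covariate dropped.
2. State that patient random slopes are fitted. Dropping the covariate alone is not enough: with intercepts only and slope SD 0.1, the ratio is still about 0.91-0.96 with 3-6 scores.
3. Report a clinic-robust SE with a small-sample correction for 34 clinics as a check.
4. Do not make a common index mean across arms the preferred model. It gives an SE 3-8% smaller than as written but assumes that the arms are equal at index, and Measures of Covariates itself anticipates imbalance from randomising clinics. For an assumed persistent index difference of 0.1 SD, with about 6,600 patients in 34 clinics, null rejection would be 12-14%, 7-8% and about 5% at clinic ICC 0.001, 0.005 and 0.02. The documents do not show such an imbalance.
5. A model of post-index scores only, with the index value as covariate, is also calibrated when random slopes are fitted. Its slope SE is 13-50% larger with 3 or more scores, so it belongs among sensitivity analyses.

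The cost is one changed model statement and one extra results table, with no new data. The note on Hypothesis 5 shows that efficacy results were already known, so the planned result must still be reported, with the corrected model beside it and labelled post hoc.
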